#### **6.4.2. Unsolicited Treatment-emergent Adverse Events**

A treatment-emergent AE (TEAE) is defined as any event occurring during the study not present before exposure to the IP or any event already present that worsens after exposure to IP. Worsening of a pre-existing condition after vaccination will be reported as a new AE.

Adverse events will also be evaluated by the investigator for the coexistence of MAAE which is defined as an AE that leads to an unscheduled visit to a healthcare practitioner.

Unsolicited AEs will be coded by PT and SOC using MedDRA and summarized by vaccination group.

Unsolicited AEs will be collected for up to 28 days after IP dose; SAEs, MAAEs, AESIs, and AEs leading to withdrawal will be collected throughout the study. Analyses of unsolicited AE will be provided for up to 28 days after vaccination unless otherwise specified. SAE, AESI, MAAE, and AE leading to discontinuation from the study up to 28 days after vaccination and throughout the study (up to Day 181/End of Study) will be summarized. Up to 28 days after vaccination period will be used as the primary analysis period for Unsolicited AEs.

All summary tables (except for the overall summary of AEs) for unsolicited AEs will be presented by SOC and PT or by PT only for TEAEs with counts of participants included. SOC will be displayed in internationally agreed order. PTs will be displayed in descending order of frequency in the mRNA-1073 CCI group and then alphabetically within SOC. When summarizing the number and percentage of participants with an event, participants with multiple occurrences of the same AE or a continuing AE will be counted once. Only the maximum severity level will be presented in the severity summaries, and the strongest relationship level will be presented in the relationship summaries.

Percentages will be based upon the number of participants in the Safety Set within each treatment group.

##### **6.4.2.1. Overview of Unsolicited TEAEs**

An overall summary of unsolicited TEAEs up to 28 days after IP injection including the number and percentage of participants, along with the number of events, by vaccination group who experience the following will be presented:

- Any unsolicited TEAEs
- Any unsolicited serious TEAEs
- Any unsolicited AESI
- Any unsolicited TEAEs that are medically-attended
- Any unsolicited TEAEs leading to discontinuation from participation in the study
- Any unsolicited severe TEAEs
- Any unsolicited TEAEs that are fatal

The table will also include number and percentage of participants with unsolicited TEAEs that are treatment-related in each of the above categories.

The overall summary will be also provided considering all reported events up to End of Study.

In addition, separate listings containing individual subject adverse event data for unsolicited TEAEs leading to discontinuation from participation in the study, serious AEs, serious treatment-related AEs, and unsolicited treatment-related medically-attended AEs will be provided. Listing of deaths including cause of death, and listing of TEAEs in subjects who died will be provided.

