## 3. Study Endpoints

### 3.1. Primary Endpoints

The primary objective will be evaluated by the following endpoints:

- Frequency and grade of each solicited local and systemic reactogenicity AR during a 7-day follow-up period post vaccination
- Frequency and severity of any unsolicited adverse events (AEs) during the 28-day follow-up period post vaccination
- Frequency of any serious adverse events (SAEs), adverse events of special interest (AESIs), medically attended adverse events (MAAEs), and AEs leading to discontinuation from Day 1 to Day 181/EoS

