### 6.4.1. Solicited Adverse Reactions

An AR is any AE for which there is a reasonable possibility that the test product caused the AE. The term “Solicited Adverse Reactions” refers to selected signs and symptoms occurring after injection administration during a specified post-injection follow-up period (day of injection and 6 subsequent days). An eDiary will solicit daily the participant on the occurrence and intensity of selected signs and symptoms using a pre-defined structured checklist.

The following local ARs will be solicited by the eDiary: injection site pain, injection site erythema (redness), injection site swelling/induration (hardness), and underarm gland swelling or tenderness.

The following systemic ARs will be solicited by the eDiary: headache, fatigue, myalgia (muscle aches all over the body), arthralgia (aches in several joints), nausea/vomiting, chills, and fever.

The solicited ARs will be graded based on the grading scales presented in Table 6 in the protocol, modified from the Toxicity Grading Scale for Healthy Adult and Adolescent Volunteers Enrolled in Preventative Vaccine Clinical Trials ([DHHS 2007](#)).

If a solicited local or systemic AR continues beyond 7 days post-injection, the subject will be prompted to capture solicited local or systemic AR in the eDiary until resolution, not to exceed 28 days after study injection.

All solicited ARs (local and systemic) will be considered causally related to dosing.

Analyses of solicited ARs will be provided by vaccination group based on the Solicited Safety Set. Summaries of local solicited ARs will be also presented by vaccination group and injection content received in the corresponding side/deltoid.

The number and percentage of participants with any solicited local ARs, solicited systemic ARs, and solicited ARs during the 7-day follow-up period after the injection will be summarized, along with the number of events under each category. A two-sided 95% exact CI using the Clopper-Pearson method will be provided for the percentage of participants who reported any solicited local AR, solicited systemic AR, or any solicited AR.

The number and percentage of participants who reported each individual solicited local AR and solicited systemic AR during the 7-day follow-up period after injection will be provided by severity grade.

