#### **6.4.2.2. TEAEs by System Organ Class and Preferred Term**

The following summary tables of TEAEs up to 28 days after IP injection will be provided by SOC and PT using frequency counts and percentages (i.e. number and percentage of participants with an event) and number of events:

- All unsolicited TEAEs
- All unsolicited TEAEs that are treatment-related
- All unsolicited AESI

- All unsolicited AESI that are treatment-related
- All unsolicited serious TEAEs
- All unsolicited serious TEAEs that are treatment-related
- All unsolicited TEAEs leading to discontinuation from participation in the study
- All unsolicited severe TEAEs
- All unsolicited severe TEAEs that are treatment-related
- All unsolicited AEs that are medically-attended

Summary tables of all unsolicited TEAEs, serious AEs, treatment-related SAEs, MAAEs, and TEAE leading to discontinuation from participation in the study will be also be provided by SOC and PT considering all events reported throughout the study.

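### The 28-day SAE, AESI, MAAE and discontinuation tables are limited to unsolicited events while the primary endpoint covers any such event, so a qualifying solicited reaction can go uncounted

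*SAP*

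**What the plan says.** For the period Day 1 to Day 181/EoS, SAP 3.1 sets the third primary endpoint as "Frequency of any serious adverse events (SAEs), adverse events of special interest (AESIs), medically attended adverse events (MAAEs), and AEs leading to discontinuation". The second primary endpoint is expressly about unsolicited AEs; the third is not.

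Section 6.4.1 makes a reaction a kind of AE: "An AR is any AE for which there is a reasonable possibility that the test product caused the AE". It adds: "All solicited ARs (local and systemic) will be considered causally related to dosing". Section 6.4.2 refers to an "MAAE which is defined as an AE that leads to an unscheduled visit to a healthcare practitioner", with no exception for solicited reactions.

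The same section gives a general rule that "SAE, AESI, MAAE, and AE leading to discontinuation from the study up to 28 days after vaccination and throughout the study" will be summarized. That sentence does not use the word 'unsolicited', although the section heading does.

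The detailed specifications are narrower. The 28-day overview in 6.4.2.1 has the row "Any unsolicited TEAEs that are medically-attended", and its serious, AESI, discontinuation, severe and fatal rows are qualified in the same way. The 28-day SOC/PT list in 6.4.2.2 includes "All unsolicited serious TEAEs", and every other bullet there carries the same adjective. Among the listings in 6.4.2.1, the one for discontinuation events is limited to unsolicited TEAEs, and the MAAE listing reads "unsolicited treatment-related medically-attended AEs will be provided". The listing of serious AEs has no such qualifier of its own.

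**The concern.** A participant who develops fever or vomiting on Day 2 and makes an unscheduled visit to a practitioner has a solicited reaction that is also an MAAE under the SAP's own definition. The same holds if the reaction is serious or causes withdrawal. Read literally, the filter in the 28-day tables leaves that participant out of the MAAE, SAE or discontinuation row.

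Two features make this worth settling before programming:

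- Section 6.1 makes the 28 days after vaccination the primary period for safety analyses other than solicited reactions, and the interim analysis in 6.7.1 uses data up to Day 29. The expressly filtered tables are therefore those for the primary period, and they cover the interim window. Solicited reactions also arise in this window.
- Because 6.4.1 deems every solicited reaction causally related, any event lost in this way is vaccine-related by the SAP's own rule.

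**Working it through.** The point rests on wording, so the relevant places are set side by side first.

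| Place in SAP | Period | Limited to unsolicited? |
|---|---|---|
| 3.1, third primary endpoint | Day 1 to Day 181/EoS | No |
| 6.4.2, general summary rule | 28 days and to EoS | Not expressly; it sits under a heading about unsolicited events |
| 6.4.2.1, overview | 28 days | Yes, every row |
| 6.4.2.1, overview repeated | To EoS | Unclear: it takes in all reported events, which may lift the limit or only extend the period |
| 6.4.2.1, listings of discontinuation events and treatment-related MAAEs | Not stated | Yes |
| 6.4.2.1, listing of serious AEs | Not stated | Not expressly |
| 6.4.2.2, SOC/PT bullets | 28 days | Yes, every bullet |
| 6.4.2.2, closing sentence on SOC/PT tables | Throughout the study | Not expressly for SAEs, MAAEs and discontinuations; AESIs are not named |

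**Step 1: can a solicited reaction meet the endpoint?** Yes. An AR is an AE (6.4.1), an MAAE is defined on an AE (6.4.2), and 3.1 counts any such event.

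**Step 2: do the 28-day tables count it?** Not as written. The adjective is on every row and bullet. The listing sentence in 6.4.2.1 drops it for serious AEs and restores it for MAAEs, so a programmer would reasonably treat it as a filter.

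**Step 3: does a solicited-reaction table recover it?** No. Section 6.4.1 provides counts, severity grade, onset, duration, persistence beyond 7 days and delayed onset. It provides nothing by seriousness, medical attendance or withdrawal.

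**Step 4: do the tables agree with each other?** They need not. The 6.4.2 rule promises SAE, AESI, MAAE and discontinuation summaries to 28 days without an express limit, but the only 28-day tables specified are limited. The throughout-study SOC/PT tables could then include events within the first 28 days that the 28-day tables leave out.

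**Step 5: possible size.** The only design figures in the SAP are in Table 2 (section 4.3), the probability of at least one AE, 1 − (1 − p)^n. They reproduce:

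- n = 50, p = 0.05: 1 − 0.95^50 = 0.9231 (stated 92.3%)
- n = 50, p = 0.03: 1 − 0.97^50 = 0.7819 (stated 78.2%)
- n = 100, p = 0.03: 1 − 0.97^100 = 0.9524 (stated 95.2%)
- n = 100, p = 0.02: 1 − 0.98^100 = 0.8674 (stated 86.7%)

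Table 2 concerns any AE. The SAP gives no rate for solicited reactions that are serious, medically attended or lead to withdrawal. Purely as an assumption, let q be the share of participants with such a reaction, and suppose none is counted. The expected loss is n × q, and the chance of losing at least one participant is 1 − (1 − q)^n:

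| Arm size | q | Expected loss | Chance of losing at least one |
|---|---|---|---|
| 100 | 0.5% | 0.5 | 39% |
| 100 | 1% | 1.0 | 63% |
| 100 | 2% | 2.0 | 87% |
| 100 | 3% | 3.0 | 95% |
| 50 | 0.5% | 0.25 | 22% |
| 50 | 3% | 1.5 | 78% |

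These figures show what the filter could do; they do not estimate what it will do.

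**The case against.** The strongest reply is that the tables whose period matches the endpoint are not the filtered ones. The closing sentence of 6.4.2.2 names serious AEs, treatment-related SAEs, MAAEs and discontinuation TEAEs over the whole study without repeating the adjective, whereas the 28-day bullets repeat it every time. The 6.4.2 rule and the serious AE listing point the same way. This stands. A reader might infer that such reactions are left out of the primary endpoint altogether, but the SAP does not establish that.

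Second, the protocol is not shown and may require such reactions to be recorded as AEs as well. The TEAE definition in 6.4.2 does not exclude solicited symptoms. This also stands, so it cannot be said that the 28-day tables would certainly miss every such event. It does not close the gap, because the SAP never says whether an AE record of that kind counts as unsolicited, and the filter depends on exactly that.

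Third, a reader might infer that the filter flatters the most reactogenic arm. Under-counting could plausibly rise with reactogenicity, but 6.4.1 reports each arm's solicited reactions in full, by grade and with exact confidence intervals for the overall rates, and 4.2 states that no hypotheses are tested. The documents do not support a claim of a distorted comparison. What 6.4.1 does not show is which of those reactions were serious, medically attended or led to withdrawal.

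**Conclusion.** The concern holds as an inconsistency with a practical consequence. As written, the 28-day overview, the 28-day SOC/PT tables and the two listings are narrower than the primary endpoint and than the SAP's own summary rule. A qualifying solicited reaction can be left out of the primary-period tables and of the same tables at the interim, nothing in the solicited section recovers it, and tables of the same events can give different counts.

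Omission from the Day 1 to Day 181 endpoint remains possible only. It depends on how the throughout-study sentence and the end-of-study overview are read, and on recording rules that are not in this document. The number of participants affected is unknown, and the range of 0.5 to 3 per 100 rests wholly on the assumed rate of 0.5% to 3%. The change should be made because it is cheap and the endpoint is primary, not because a given loss has been shown.

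**What to change.** In 6.4.2.1 and 6.4.2.2:

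- Define the SAE, AESI, MAAE, discontinuation and fatal rows, with their treatment-related counts, over all AEs (solicited ARs and unsolicited TEAEs), both for 28 days and for Day 1 to Day 181/EoS.
- Keep 'unsolicited' only for the rows on any unsolicited TEAE and on severe unsolicited TEAEs, with their treatment-related counts. The treatment-related counts under the SAE, AESI, MAAE, discontinuation and fatal rows must not keep the limit. Otherwise a serious solicited reaction would count as an SAE but not as a treatment-related one, against the causality rule in 6.4.1.
- Remove 'unsolicited' from the MAAE and discontinuation listings.
- Add a footnote that some events also appear in the solicited-reaction tables.

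The cost is SAP wording and a data-set filter. Section 6.4 already has solicited ARs coded by SOC and PT, so no new coding is needed. The downside is slightly higher event counts and some events displayed twice.

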#### **6.4.2.2. TEAEs by System Organ Class and Preferred Term**

The following summary tables of TEAEs up to 28 days after IP injection will be provided by SOC and PT using frequency counts and percentages (i.e. number and percentage of participants with an event) and number of events:

- All unsolicited TEAEs
- All unsolicited TEAEs that are treatment-related
- All unsolicited AESI

- All unsolicited AESI that are treatment-related
- All unsolicited serious TEAEs
- All unsolicited serious TEAEs that are treatment-related
- All unsolicited TEAEs leading to discontinuation from participation in the study
- All unsolicited severe TEAEs
- All unsolicited severe TEAEs that are treatment-related
- All unsolicited AEs that are medically-attended

Summary tables of all unsolicited TEAEs, serious AEs, treatment-related SAEs, MAAEs, and TEAE leading to discontinuation from participation in the study will be also be provided by SOC and PT considering all events reported throughout the study.

#### **6.4.2.3. TEAEs by Preferred Term**

Tables of all unsolicited TEAEs will be provided by PT sorted in a descending order according to the frequency of the mRNA-1073 CCI group.

#### **6.4.2.4. TEAEs by Toxicity Grade**

The following summary tables of TEAEs will be provided by SOC, PT and the maximum severity or toxicity Grade using frequency counts and percentages:

- All unsolicited TEAEs
- All unsolicited TEAEs that are treatment-related

#### **6.4.2.5. Subgroup Analysis of TEAEs**

The overview of TEAEs and the summary of unsolicited TEAEs by SOC and PT will be provided for the following subgroup:

- Age group (18 to 49 years old and 50 to 75 years old)

#### **6.4.3. Vital Sign Measurements**

Vital signs will be collected only at Screening and on the day of vaccination (Day 1), once before and at least 60 minutes after vaccination. Vital signs will be collected at other clinical visits only in conjunction with a symptom-directed physical examination.

Vital sign measurements, including systolic and diastolic blood pressures, heart rate, respiratory rate and body temperature will be presented in a data listing. The values meeting the toxicity grading criteria will be flagged in the data listing.

The abnormalities meeting the toxicity grading criteria (Grade 3 or higher) in Appendix F in any vital sign measurement will be listed separately. If a subject has a vital sign result with Grade 3 or higher abnormality after injection visit, then all results of that specific vital sign for that subject will be presented in the listing.

Observed values and changes from pre-injection to post-injection at Day 1 for all vital sign measurements will be summarized by vaccination group as defined in Section 4. Shift from baseline in the toxicity grades to post-injection result at Day 1 will also be summarized by vaccination group.

#### **6.4.4. Clinical Laboratory Evaluations**

Safety laboratory assessments (total white blood cell count, hemoglobin, platelets, ALT, AST, creatinine, alkaline phosphatase, and total bilirubin) will be assessed at Screening and Day 8. Individual results of safety laboratory assessments will be presented in a data listing.

For continuous hematology and serum chemistry parameters, the observed values and changes from baseline will be summarized at each visit by vaccination group as defined in [Section 6.1](#). Hematology and chemistry toxicity grades will be summarized using a shift table from baseline to Day 8 by vaccination group.

A pregnancy test will be performed on all female participants of childbearing potential at the Screening Visit and before vaccine administration on Day 1 via point-of-care urine, and as needed at unscheduled visits (urine or blood pregnancy test based on the investigator's discretion). A follicle stimulating hormone (FSH) test may be performed at the Screening Visit (Day 0), as necessary and at the discretion of the investigator, to confirm postmenopausal status.

#### **6.4.5. Physical Examinations**

A full physical examination, including height and weight, will be performed at the Screening Visit. The full examination will include assessment of skin, head, ears, eyes, nose, throat, neck, thyroid, lungs, heart, cardiovascular system, abdomen, lymph nodes, and musculoskeletal system and extremities.

Symptom-directed physical examinations may be performed at other time points at the discretion of the investigator. Individual results of physical examination will be presented in a data listing.

## 6.5. Immunogenicity Analysis

The analyses of immunogenicity will be based on the PP set. If the number of participants in the FAS and PP set differs (defined as the difference divided by the total number of participants in the PP set) by more than 10%, supportive analyses of immunogenicity may be conducted using the FAS.

### 6.5.1. Immunogenicity Assessments

Blood samples for immunogenicity assessments will be collected at the time points indicated in the SoE. Immunogenicity assessments will be performed for all participants.

Immune responses to SARS-CoV-2 vaccine antigens will utilize either pseudovirus neutralization (PsVNA) nAb assay or multiplex bAb assay, depending on the timing of data delivery. The following analytes will be measured:

- Influenza: Serum antibody level as measured by HAI assay
- Influenza: Serum nAb level as measured by microneutralization assay as potential substitution to the HAI assay
- SARS-CoV-2: Serum nAb titers as measured by PsVNA assay and potentially serum binding antibody titers by ELISA or multiplex assay specific to the SARS-CoV-2 proteins
- Cellular immunogenicity in a subset of participants

### 6.5.2. Immunogenicity Analysis

The following immunogenicity endpoints will be evaluated:

- GMT and GMFR at Day 29 compared with Day 1 (baseline) by HAI assay for influenza and PsVNA (or binding antibody assay) for SARS-CoV-2
- Influenza: Percentage of participants with seroconversion, defined as a Day 29 titer  $\geq 1:40$  if baseline is  $< 1:10$  or a 4-fold or greater rise if baseline is  $\geq 1:10$  in anti-HA antibodies measured by HAI assay

- SARS-CoV-2: Percentage of participants with seroresponse, defined as a Day 29 titer  $\geq 4$ -fold if baseline is  $\geq$  LLOQ or  $\geq 4 \times$  LLOQ if baseline titer is  $<$  LLOQ in nAb titers measured by PsVNA (or binding antibody assay).
- GMT and GMFR compared with Day 1 (baseline) by HAI for influenza and PsVNA (or binding antibody assay) for SARS-CoV-2
- Percentages of participants with seroconversion (influenza) and seroresponse (SARS-CoV-2) as defined below

For the immunogenicity endpoints, the geometric mean of specific antibody titers with corresponding 95% CI at each time point and the geometric mean fold rise of specific antibody titers with the corresponding 95% CI at each post-baseline time point over pre-injection baseline at Day 1 will be provided by treatment arm.

Descriptive summary statistics, including median, minimum, and maximum, will also be provided. The geometric mean (GM) will be calculated using the following formula (Nauta, 2011):

$$2^{\left\{ \frac{\sum_{i=1}^n \log_2(t_i)}{n} \right\}}$$

where  $t_1, t_2, \dots, t_n$  are  $n$  observed immunogenicity titers or levels.

The GMFR measures the changes in immunogenicity titers or levels within participants. The GMFR will be calculated using the following formula:

$$2^{\left\{ \frac{\sum_{i=1}^n \log_2(v_{ij}/v_{ik})}{n} \right\}} = 2^{\left\{ \frac{\sum_{i=1}^n \log_2(v_{ij}) - \log_2(v_{ik})}{n} \right\}}$$

where, for  $n$  participants,  $v_{ij}$  and  $v_{ik}$  are observed immunogenicity titers or levels for participant  $i$  at time points  $j$  and  $k$ ,  $j \neq k$ .

The 95% CIs for GMT and GMFR will be calculated based on the t distribution of the log-transformed values then back transformed to the original scale for presentation, unless otherwise specified.

The model-based GM titer will be estimated based on an analysis of covariance (ANCOVA) model. In the ANCOVA model, the log-transformed antibody titer at a post baseline timepoint (Day 29) are treated as a dependent variable, with the treatment group

as an explanatory variable and the log-transformed baseline antibody titer as a covariate, adjusting for the stratification factor(s) as appropriate, that is, age groups (18 to 49 years old, and 50 to 75 years old of age).

The GMT will be estimated by the geometric least square mean (GLSM) from the ANCOVA model for each treatment group and corresponding 95% CI will be provided.

For each pair of between-group comparison specified in Table 5, the GMR (ratio of GMTs) between the two treatment groups in each pair will be estimated from the ANCOVA model, with 95% CI provided accordingly.

For summarizations of geometric mean titer, antibody titers reported as below the lower limit of quantification (LLOQ) will be replaced by  $0.5 \times \text{LLOQ}$ . Values that are greater than the upper limit of quantification (ULOQ) will be converted to the ULOQ.

For mRNA-1010, seroconversion rate from baseline will be provided with a 2-sided 95% CI using the Clopper-Pearson method at each post-baseline time point. Rate of seroconversion is defined as the proportion of participants with either a pre-vaccination HAI titer  $< 1:10$  and a post-vaccination HAI titer  $\geq 1:40$  or a pre-vaccination HAI titer  $\geq 1:10$  and a minimum 4-fold rise in post-vaccination HAI antibody titer.

For mRNA-1273, seroresponse is defined as either participants with GMFR in nAb or bAb titers of  $\geq 4$  folds at Day 29 compared to Day 1 in those with baseline titer  $\geq \text{LLOQ}$ , or Day 29 titer  $\geq 4 \times \text{LLOQ}$  if baseline titer is  $< \text{LLOQ}$ . The immunogenicity of mRNA-1073 will follow the same rules as mRNA-1010 and mRNA-1273.

For each pair of between-group comparison specified in Table 5, the difference of seroresponse/seroconversion rate (SRR/SCR) between the two treatment groups in each pair at Day 29 will be provided, with 95% CI estimated using Miettinen-Nurminen method.

Table 5. Exploratory between-group Immunogenicity comparisons

Influenza					
Treatment Group	Group #4	Group #5	Group #6	Group #3	Group #2
Group #5	#4 v.s. #5	NA	NA	NA	NA
Group #6	#4 v.s. #6	#5 v.s. #6	NA	NA	NA

Group #3	#4 v.s. #3	#5 v.s. #3	#6 v.s. #3	NA	NA
Group #2	#4 v.s. #2	#5 v.s. #2	#6 v.s. #2	#3 v.s. #2	NA
SARS-CoV-2					
Treatment Group	Group #4	Group #5	Group #6	Group #3	Group #1
Group #5	#4 v.s. #5	NA	NA	NA	NA
Group #6	#4 v.s. #6	#5 v.s. #6	NA	NA	NA
Group #3	#4 v.s. #3	#5 v.s. #3	#6 v.s. #3	NA	NA
Group #1	#4 v.s. #1	#5 v.s. #1	#6 v.s. #1	#3 v.s. #1	NA

Note: the 6 treatment groups can be found in [Table 1](#).

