## 4.2. Statistical Hypotheses

No formal hypotheses will be tested. All analyses will be descriptive using observed data only, and presented by vaccine group.

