#### 4.4. Randomization

Randomization will be performed using an interactive response technology (IRT). Participants will be randomized in a CCI [REDACTED] to receive mRNA-1273 (CCI [REDACTED]) + placebo (50 participants), mRNA-1010 (CCI [REDACTED]) + placebo (100 participants), mRNA-1010 (CCI [REDACTED]) + mRNA-1273 (CCI [REDACTED]) co-administration (100 participants), mRNA-1073 (CCI [REDACTED]) + placebo (100 participants), mRNA-1073 (CCI [REDACTED]) + placebo (100 participants), or mRNA-1073 (CCI [REDACTED]) + placebo (100 participants). Randomization will be stratified by age (18 to 49 years old and 50 to 75 years old, balanced across the 2 age groups within each vaccination group).

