### **5.3. Per Protocol (PP) Set**

The PP set consists of all participants in the FAS who comply with the injection schedule, comply with the timings of immunogenicity blood sampling to have a baseline and at least 1 post-injection assessment and a Day 29 assessment, do not have influenza or SARS-CoV-2 infection at baseline and post-baseline up to Day 29 (as documented by positive RT-PCR testing result), and have no major protocol deviations and/or prohibited concomitant medication use (in the Protocol section 6.5.3) that are prespecified with impacts on the immune response and should be excluded from the PP analysis set. The PP set will be used as the primary analysis set for analyses of immunogenicity unless otherwise specified. Participants will be analyzed according to the group to which they were randomized.

Subjects with dosing error will be considered as having a protocol deviation. However, the determination of whether to include/exclude subjects from the PP Set due to dosing error will be based on the dosage difference (in  $\mu\text{g}$ ) between the actual dose received and the randomized dose. The PP Set exclusion criteria for subjects with dosing error are described below in Table 3.

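### The Day 29 seroconversion and seroresponse differences should use the randomised age strata, as the GMRs for the same pairs do; the arms in each antigen's ANCOVA should also be named

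*SAP*

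**What the plan says.** Section 4.4 of the SAP: "Randomization will be stratified by age (18 to 49 years old and 50 to 75 years old, balanced across the 2 age groups". That balance is meant to hold inside every arm.

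Section 6.5.2 specifies two kinds of between-group contrast at Day 29, both for the pairs in its Table 5:

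- **GMR.** This comes from an ANCOVA with baseline titre as covariate, "adjusting for the stratification factor(s) as appropriate, that is, age groups". The model's output is described as follows: "The GMT will be estimated by the geometric least square mean (GLSM) from the ANCOVA model for each treatment group".
- **Difference in seroresponse or seroconversion rate.** This is given "with 95% CI estimated using Miettinen-Nurminen method". No strata, weights or age term are named here or elsewhere in the SAP.

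The analysis set is fixed in Section 5.3: "The PP set will be used as the primary analysis set for analyses of immunogenicity unless otherwise specified". Section 4.2 sets the level of inference: "No formal hypotheses will be tested". Table 5 is itself labelled exploratory.

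**The concern.** One pair of arms at one visit would get an age-adjusted titre ratio and an age-unadjusted rate difference, with no reason given. This has two consequences.

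1. **Precision.** Stratified randomisation balances age between arms. An analysis that ignores the strata still counts between-age variation as noise, so its interval is wider than it needs to be whenever response differs by age.
2. **Age mix.** The per-protocol set is formed by exclusions after randomisation: infection up to Day 29, missing samples, deviations and dosing errors. If these fall unevenly on the age groups in two arms, the unstratified difference carries an age effect. The adjusted GMR for the same pair does not.

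A secondary point concerns the ANCOVA. Section 6.5.1 has immunogenicity assessed in all participants, so Group 1 (no influenza vaccine) has influenza titres and Group 2 (no SARS-CoV-2 vaccine) has SARS-CoV-2 titres. Table 5 lists five arms per antigen, but only as pairs to compare. The model text speaks only of treatment groups in general. A programmer could fit all six arms, five arms, or each pair alone. Including the arm without the antigen changes the common baseline slope and the residual variance, and so every GMR interval.

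**Working it through.** **Inputs from the SAP.** Arm sizes are 50 (Group 1) and 100 (Groups 2 to 6), from Table 1. There are two age strata, balanced within arm (Section 4.4). The SAP states no figure for the rate difference. Its only design figures, in Table 2, concern adverse events and reproduce from 1 − (1 − p)^n: 92.3%, 78.2%, 95.2% and 86.7%.

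**Assumptions.** The SAP gives no response rates, SDs or slopes, so all of those below are assumed. Each arm is half in each age group.

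**Interval.** With strata k:

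- D = Σ w_k (p1k − p0k), where w_k is proportional to n1k·n0k/(n1k + n0k) and the weights sum to 1.
- V_k(d) = [p̃1(1 − p̃1)/n1k + p̃0(1 − p̃0)/n0k] × N_k/(N_k − 1), with p̃ the estimates restricted to p1 − p0 = d.
- The limits are the values of d where (D − d)/√(Σ w_k² V_k(d)) = ±1.96.

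The unstratified interval is the same with a single stratum.

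**1. Width.** 100 v 100, overall rate 65%, no true difference, 3000 simulated trials per case. The last column is a large-sample check: √(pooled variance / mean within-stratum variance), where the pooled variance is 0.65 × 0.35 = 0.2275.

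| Rate, younger/older | Mean width, unstratified (points) | Mean width, stratified (points) | Unstratified wider by | Large-sample ratio |
|---|---|---|---|---|
| 70%/60% | 26.22 | 26.10 | 0.5% | √(0.2275/0.2250) = 1.006 |
| 75%/55% | 26.22 | 25.72 | 2% | √(0.2275/0.2175) = 1.023 |
| 80%/50% | 26.23 | 25.06 | 5% | √(0.2275/0.2050) = 1.053 |
| 85%/45% | 26.24 | 24.13 | 9% | √(0.2275/0.1875) = 1.102 |

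With no age effect the widening is 0%. Coverage is 95.9% unstratified against 95.4% stratified at 75%/55%, and 97.0% against 95.2% at 85%/45%. For 100 v 50 (pairs with Group 1), the stratified-to-unstratified width ratio is 0.982 at 75%/55% and 0.924 at 85%/45%, a widening of 2% and 8%.

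**2. Age mix in the per-protocol set.** The shift is the difference between arms in the share of younger participants, times the age gap in response.

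- Five older lost from one arm and five younger from the other (95 v 95): 50/95 − 45/95 = 5.26 points. Times 0.20 gives 1.1 points (75%/55%); times 0.40 gives 2.1 points (85%/45%).
- Eight older lost from one arm only (92 v 100): 50/92 − 50/100 = 4.35 points. This gives 0.9 and 1.7 points.
- A harsher case, 50 younger and 40 older against 40 and 50, with rates of 70%/40% in both arms: the unstratified difference is 3.3 points (−11.2 to 17.7), and the stratified one is 0.0 (−13.8 to 14.1).

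In the first two cases the stratified difference stays on average within 0.2 points of zero. For scale, the half-width at 100 v 100 is 1.96 × √(2 × 0.2275/100) = 13 points.

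**3. Arms in the ANCOVA.** A simple illustration: take a log2 residual SD of 1.5 in arms given the antigen and 0.5 in the arm not given it.

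- Influenza, adding Group 1: √[(500 × 2.25 + 50 × 0.25)/550] = 1.44, about 4% below 1.5.
- SARS-CoV-2, adding Group 2: √[(450 × 2.25 + 100 × 0.25)/550] = 1.37, about 8% below 1.5.

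A simulation that also lets the baseline slope differ shows both directions. It used 4000 runs, residual SD 0.40 log10 and slope 0.5 in antigen arms; SD 0.10 to 0.40 and slope 0.95 in the other arm; baseline SD 0.4 to 0.6.

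| Contrast | Six-arm v five-arm width | Six-arm coverage |
|---|---|---|
| SARS-CoV-2, #4 v #1 | 7% narrower to 3% wider | 92.8% to 95.2% |
| Influenza, #4 v #3 | 3% narrower to 2% wider | 94.2% to 95.3% |

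Five-arm coverage was 94.5% to 95.6% throughout.

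**The case against.** The strongest reply is that nothing here is an error. An unstratified Miettinen-Nurminen interval is valid, the SAP never promises age-adjusted rates, and it is silent on strata rather than excluding them. The age adjustment in the ANCOVA is itself hedged, being made only as appropriate. Section 6.1 also plans tables by age group, which would show a response gradient or a shifted age mix. There is no hypothesis, margin or decision rule. A widening of 9% needs a 40-point age gap, and exclusions unrelated to arm and age give an expected shift of zero. The harshest case loses 10 of 100 per arm. At that rate across the study, the two sets would differ by 10/90 = 11%, beyond the 10% at which Section 6.5 allows supportive analyses in the FAS.

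Much of this stands, and it limits the stakes. It does not remove the point. By-age tables show two separate results and do not supply one age-adjusted difference. The FAS analysis is only optional. If the silence is meant to allow stratification, the weights are missing.

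On the ANCOVA, fitting the five arms in Table 5 is a natural reading, though not a stated one. The influenza effect is close to simulation error: the standard error of coverage is √(0.95 × 0.05/4000) = 0.34 points. Only the SARS-CoV-2 contrast with Group 1 shows a clear loss of coverage, and only at the edge of the assumed range.

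**Conclusion.** The point holds, as a modest improvement rather than the correction of an invalid method. For the same pairs, the plan adjusts the titre ratio for the randomisation factor and specifies no such adjustment for the rate difference. The cost of leaving age out is an interval 0.5% to 9% wider for age gaps of 10 to 40 points. Under uneven per-protocol losses there is also a displacement of about 1 to 2 points, or 3 in a harsh case. These sizes rest entirely on assumed response rates. With no age gradient, both effects vanish.

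The unnamed ANCOVA arms are a secondary gap in specification. Under the assumed SDs and slopes, a six-arm fit changes interval widths by between −7% and +3%. Since no tests are planned, the estimates and intervals are all a reader will have from these contrasts, so they should be consistent and fully specified.

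**What to change.** In Section 6.5.2:

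1. State that the difference in seroconversion or seroresponse rate uses the Miettinen-Nurminen interval stratified by the two randomised age groups. Give the stratum weights, for example n1·n2/(n1 + n2).
2. State that each antigen's ANCOVA is one model with only the five arms Table 5 lists for it: Groups 2 to 6 for influenza, and Groups 1 and 3 to 6 for SARS-CoV-2. Report the remaining arm with the t-based GMT and GMFR already planned.

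The cost is two sentences in the SAP, a strata statement and a data restriction in the programs. No new data are needed. The change should be made before unblinding.
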